6.2.2. Measurement of Vibratory Threshold

Vibratory threshold is measured by a Rydel Seiffer graduated tuning fork. The two arms of this tuning fork bear calibrated weights at their extremities. A triangle and an arbitrary scale from 0 (minimum score) to 8 (maximum score) imprinted on the weights allow assessment of vibration threshold. Once the arms are swinging, the fork vibrates at 64 Hz and the triangles on the weights appear double. The intersection of these two virtual triangles moves from 0 to 8 in an exponential way with decreasing vibration amplitude of the arms. The vibration extinction threshold is considered as the nearest value to the apparent point of intersection of the virtual triangles when the subject indicates that vibration is no longer perceived.

6.2.3. Time to Sway

With patient staying with their feet together, they will be asked to close their eyes. Time until the onset of a postural sway will be recorded.

6.2.4. Timed Walk Test

Subjects will be asked to walk a marked, pre-defined 6-meter distance at a normal speed and the time required for time walk will be recorded.

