Usefulness of tDCS in modulating sensory functions has been reported before. For example, it has been shown that anodal stimulation of S1 can increase somatosensory evoked potential (SEP) while cathodal stimulation will reduce it[28]. It has been shown that performance of healthy subjects as well as patients with multiple sclerosis (MS) in a tactile task can be enhanced by anodal stimulation of S1[29]. It has also been reported that stimulation of M1 cortex with tDCS can increase SEP. Stimulation of motor cortex has also been shown to enhance the thermal and mechanical sensation as tested by quantitative sensory testing[30]. Additionally a dual hemispheric protocol -during which S1 on one side is stimulated and on the other side is inhibited to block the interhemispheric inhibitory pathways- has been tested in healthy individuals and has been shown to improve performance in tactile spatial discrimination tasks[31]. Interestingly, the effects of tDCS on sensation can last for several minutes[32]. Effects of tDCS on gait and balance as well as improving tactile and proprioceptive sensation has been tested mostly in patients with stroke or spinal cord injury[33-37]. There is no experiment to our knowledge that has examined the effect of stimulating motor and sensory cortices on enhancing the proprioceptive signal in patients with PN. Enhancing this signal by stimulating cortical areas, theoretically can enhance the impaired proprioceptive signal from the ankle and potentially improve the balance problems caused by it. tDCS has been used before in patients with PN safely and with various degree of success for treatment of neuropathic pain, but no study has ever reported any measures of proprioception or balance[26].

In the current study, we plan to test the hypothesis that tDCS of somatosensory, motor or prefrontal cortices can enhance the proprioceptive feedback received from the ankle joints or other sensory feedback signals important for controlling balance and gait and improve these measures in patients with PN. We plan to recruit patients with PN and measure the proprioception sense of the ankle using joint position sense as well as functional measures such as timed walk and time to sway to compare in these subjects before the stimulation and after the real and sham stimulation.

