2. STUDY OBJECTIVES AND ENDPOINTS

2.1. Objectives

Primary Objective:

To evaluate the effect of tDCS on proprioception, defined as the minimum detectable angle of dorsiflexion or plantar flexion at the ankle.

Secondary Objectives:

1. To evaluate the effect of tDCS on the proprioception threshold of the big toe;
2. To evaluate the effect of tDCS on vibratory sensation threshold;
3. To evaluate the effect of tDCS on time to sway when standing with feet together and eyes closed;
4. To evaluate the effect of tDCS on timed walk test;

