2.2. Endpoints

Primary Endpoint

Minimum detectable angle of dorsiflexion and plantar flexion of the ankle.

Secondary Measures and Efficacy Endpoints

1. Time to sway when standing with feet together and eyes closed;
2. Vibratory threshold as measured by Rydel Seiffer graduated tuning fork;
3. Distance walked in a timed walk test;

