3. STUDY DESIGN

This study will be performed in patients with peripheral neuropathy who are walking independently, but have complains of balance problems such as recent falls or difficulty walking and show reduced vibratory and proprioceptive sensation during routine neurologic examination. These patients will be tested for proprioceptive and vibratory threshold at the toes and ankles before, during and after receiving anodal tDCS over sensory and motor cortices, as well as sham stimulation. Patients will be blinded and won't know if they are receiving actual stimulation or sham stimulation. Subjects will be asked to participate in 2 sessions. In one of the sessions, decided randomly, the sham stimulation will be applied and during the other session the real tDCS stimulation will be applied. Similar sets of assessments will be performed before, during and after application of real or sham stimulations.

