8. DATA ANALYSIS/STATISTICAL METHODS

8.1. Sample Size Determination

Based on the review of the literature, a sample size of 15-20 patients often time has been used to investigate the effect of tDCS. We plan to recruit 20 patients in this study.

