8.2. Analysis of Primary and Secondary Endpoints

A repeated measure ANOVA will be used to compare the outcome measures before the stimulation, after the real stimulation and after the Sham stimulation.

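### The walk outcome is described as a single timed 6-metre walk with no repeat or averaging; the mean of two walks would reduce measurement error cheaply, and the endpoint wording must be matched to it.

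*Combined protocol and SAP*

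**What the plan says.** The whole walk procedure is one sentence in Section 6.2.4, which has the patient walk a "6-meter distance at a normal speed and the time required for time walk will be recorded". It names one distance and one time. It gives no number of trials, no rule for combining trials and no description of a return walk.

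The walk is the fourth secondary objective in Section 2.1 ("To evaluate the effect of tDCS on timed walk test"). Section 2.2, however, lists the endpoint as "Distance walked in a timed walk test", which does not fit a test with a fixed distance and a recorded time.

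Section 3 describes two sessions per patient, real and sham in random order, and adds: "Similar sets of assessments will be performed before, during and after application of real or sham stimulations". Section 8.1 sets the size without a calculation: "We plan to recruit 20 patients in this study". Section 8.2 gives the analysis for all outcomes: "A repeated measure ANOVA will be used to compare the outcome measures before the stimulation, after the real stimulation and after the Sham stimulation". It has no rule for averaging repeated walks.

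**The concern.** A 6-metre walk at normal speed lasts only seconds. Chance variation in pace, and in starting and stopping the timer, therefore enters each reading. In a within-patient design it enters both the real and the sham value, and so the difference between them. With one reading per assessment nothing averages it down.

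The timed walk and time to sway are the two functional measures named at the end of Section 1.2, so they carry the gait and balance part of the hypothesis. With 20 patients, avoidable measurement error lowers the chance of detecting a gait effect and widens its interval. The walk is secondary, so the primary ankle-threshold result is not at stake.

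**Working it through.** **The plan's own figure.** The 20 patients in Section 8.1 come from common practice (15 to 20). With no alpha, power, effect size or SD stated, there is no calculation to reproduce.

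**Inputs**

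- n = 20 (Section 8.1), each patient receiving real and sham (Section 3).
- Two-sided alpha 0.05: assumed.
- Paired t-test of real versus sham: assumed, as a simplification of the three-condition repeated-measures ANOVA in Section 8.2.
- f, the share of the variance of the real-minus-sham difference due to walk-to-walk error within an assessment: not in the documents; assumed 0.2 to 0.8, with 0.1 as a low case.
- r, the correlation between the errors of two walks at the same assessment: not in the documents; 0 and 0.5 shown.

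**Step 1: effect on the variance.** The error variance of a mean of two walks is (1 + r)/2 times that of one walk. The rest of the variance, including session-to-session variation, does not change. The variance of the difference is therefore multiplied by

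v = (1 − f) + f(1 + r)/2 = 1 − f(1 − r)/2,

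that is, 1 − f/2 for r = 0 and 1 − f/4 for r = 0.5.

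**Step 2: starting effect.** Under the noncentral t with 19 degrees of freedom and critical value 2.093, 50% power at n = 20 corresponds to a difference of 0.462 SD of the single-walk difference.

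**Step 3: after averaging.** The standardised effect becomes 0.462/√v, and the number of patients with a single walk that gives the same precision is 20/v.

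| f | v, r = 0 | Power | Equivalent n | v, r = 0.5 | Power | Equivalent n |
|---|---|---|---|---|---|---|
| 0.1 | 0.95 | 52% | 21.1 | 0.975 | 51% | 20.5 |
| 0.2 | 0.90 | 54% | 22.2 | 0.95 | 52% | 21.1 |
| 0.4 | 0.80 | 59% | 25.0 | 0.90 | 54% | 22.2 |
| 0.6 | 0.70 | 65% | 28.6 | 0.85 | 57% | 23.5 |
| 0.8 | 0.60 | 72% | 33.3 | 0.80 | 59% | 25.0 |

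For example, with f = 0.4 and r = 0: v = 1 − 0.4/2 = 0.80, the effect is 0.462/√0.80 = 0.516, power is 59%, and 20/0.80 = 25.0.

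**Step 4: a second starting point.** For an effect of 0.5 SD, one walk gives 56.4% power. Two walks with independent errors give 62.1% at f = 0.25 and 76.5% at f = 0.75. The difference detectable with 80% power falls from 0.660 SD to 0.618 and 0.522 SD respectively. The pattern is the same.

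**The case against.** **One walk is read from silence.** Section 6.2.4 does not state a number of trials, and Sections 6.2.1 to 6.2.3 give no trial counts for the other tests either. This stands: the text does not rule out several walks. A single walk is still what a site would do if it followed the sentence as written. If more were intended, the number and the scoring rule are missing, and the same amendment supplies them.

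**The return walk.** A reader might infer that the patient has to walk back anyway, so that a second timing is free. The documents describe no course, turn or return. The cost should be counted as one extra 6-metre walk. That is still small, since Section 4.1 requires patients to walk without a cane or walker.

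**The size is assumption.** This also stands. Nothing in the documents shows that walk-to-walk error is a large part of the reading. Two walks taken seconds apart share the tester and the patient's momentary state, so their errors may be correlated. A low share or correlated errors leave a gain of only a few points.

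**The after-effect may be short.** Section 1.2 says that "the effects of tDCS on sensation can last for several minutes". That statement concerns sensation, not gait, and the window must also hold the rest of the battery. Seconds for one more walk are minor against minutes, but the point argues against adding many repeats. Section 3 also places assessments during stimulation without saying whether the walk is among them.

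**Repeats matter more elsewhere.** The primary ankle threshold, read in 2-degree steps with no stated trial count, would arguably benefit more. That is a fair view of priority, but no reason to leave the walk as it is.

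**Conclusion.** The point holds as a cheap improvement of low severity, with low to medium confidence. As written, the plan yields one walk time per assessment, and a mean of two would be more precise provided the errors of the two walks are not perfectly correlated. From 50% power the gain runs from 1 or 2 points at a 10% error share to 22 points at an 80% share with independent errors. These figures rest on the assumed alpha, error share, error correlation and paired t-test, and they illustrate the range; they do not estimate this trial's power.

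A reader might infer that timing two walks removes the noise. It does not: at most half of the walk-to-walk component goes, and session-to-session variation stays. Nor do the documents support reading the single walk as an error or a source of bias, because the same procedure applies to real and sham.

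One part needs no assumption. Section 2.2 names distance as the endpoint, while Section 6.2.4 fixes the distance and records time. The two must be reconciled whether or not a second walk is added.

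**What to change.** In Section 6.2.4, state that at each assessment where the walk is done, and identically in both sessions, two 6-metre walks are timed separately (for example one in each direction, with the turn not timed) and that the mean of the two times is analysed. State at which of the assessments before, during and after stimulation the walk takes place. In Section 2.2, replace distance walked with the time in seconds over the fixed 6 metres, so that the endpoint matches what is recorded.

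The cost is one or two sentences in Section 6.2.4, one changed line in Section 2.2, one more CRF field and one extra short walk per assessment. Stimulation, eligibility, visits and sample size do not change.

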6.3. Safety and Risk Assessments

Weak direct currents can be applied non-invasively, transcranially and painlessly. Such application leads to transient changes in corticomotor excitability that is fully reversible.

There are no known risks of percutaneous, transcranial DC stimulation of the brain, other than mild local discomfort at the electrode sites (much less than TMS for example). In the current published studies on humans [27, 38-42], the following objective safety data were reported:

- No heating of electrodes
- No demonstrable changes in the skin underlying electrode placement after a stimulation period similar to the one proposed in this protocol.
- Mild itching sensation in the absence of pain. Never led to stopping a study in any of the previous reports.
- No change in serum neuron-specific enolase (NSE, marker for neuronal damage) in 5 subjects immediately and 1 hour after exposure to 13 min of 1 mA anodal DC to motor cortex
- No changes in diffusion weighted or contrast-enhanced MRI and in EEG after exposure to tDCS.

Several hundred subjects so far without reporting any side effects apart from a slight itching under the electrode and a short phosphene if the stimulation was switched on or off abruptly. A review paper discussed the safety of tDCS in human. tDCS applications over motor and non-cortical areas in healthy individuals, migraine patients, post-stroke patients, and tinnitus patients ,etc. revealed the most common adverse effect after tDCS was a mild tingling sensation, followed by fatigue, then a light itching sensation under the stimulation electrodes. Not as common, but mentioned, were headache, nausea, and insomnia. The review paper concluded that tDCS is associated with very minor adverse effects in healthy humans and patients with varying neurological disorders[43]. Even higher intensities of current has been used for tDCS safely without complications[44, 45].

7. ADVERSE EVENT REPORTING

All serious adverse events will be reported to the IRB immediately by the PI.

Expected adverse events due to tDCS or TMS that will be reported in annual reviews:

- Itching sensation under the electrode (tDCS)
- Phosphene-like visual phenomenon if the DC stimulation will be switched on or off rapidly
- Slight discomfort lasting less than a second on the scalp near the TMS coil
- Twitching of the face and jaw due to the magnetic pulse, which may be unpleasant but usually not painful
- Transient headache

Exceptional adverse events due to tDCS that will be reported immediately

- Skin burn
- Seizures

8. DATA ANALYSIS/STATISTICAL METHODS

8.1. Sample Size Determination

Based on the review of the literature, a sample size of 15-20 patients often time has been used to investigate the effect of tDCS. We plan to recruit 20 patients in this study.

8.2. Analysis of Primary and Secondary Endpoints

A repeated measure ANOVA will be used to compare the outcome measures before the stimulation, after the real stimulation and after the Sham stimulation.

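### Section 8.2 does not make real minus sham the primary test, so the planned ANOVA can be significant with no tDCS effect

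*Combined protocol and SAP*

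**What the plan says.** Section 8.2 of the combined protocol and SAP consists of a single sentence: "A repeated measure ANOVA will be used to compare the outcome measures before the stimulation, after the real stimulation and after the Sham stimulation". The rationale in section 1.2 words the comparison in the same way: "to compare in these subjects before the stimulation and after the real and sham stimulation".

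Section 3 describes the design. "Subjects will be asked to participate in 2 sessions", with real stimulation in one and sham in the other, in random order. On timing it says: "Similar sets of assessments will be performed before, during and after application of real or sham stimulations". Each patient therefore has two pre-stimulation assessments, one per session.

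The primary objective in section 2.1 is: "To evaluate the effect of tDCS on proprioception, defined as the minimum detectable angle of dorsiflexion or plantar flexion at the ankle". The primary endpoint in section 2.2 is: "Minimum detectable angle of dorsiflexion and plantar flexion of the ankle". Neither names a comparator, a change score or a between-condition difference. No section gives an alpha, a post-hoc procedure, an interaction term, or a session or order term.

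**The concern.** The sham session is there to remove whatever happens in both sessions: practice with a patient-reported threshold, expectation, and the passage of time. Only a comparison of real with sham uses it for that purpose. A three-condition ANOVA (before, after real, after sham) tests whether any of the three means differ. If both post-stimulation means improve by the same amount, that null hypothesis is false and the F test will tend to reject, although tDCS has done nothing beyond sham. A contrast of real with before has the same weakness.

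Section 8.2 does not say which result decides the primary question. The false-positive risk of a tDCS claim therefore depends on which line of the ANOVA is reported once the data are in. The plan also names one pre-stimulation level where the design yields two, and does not say whether they are averaged, one is dropped, or each is paired with its own session.

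**Working it through.** **Inputs from the documents.** n = 20 (section 8.1); three conditions (section 8.2); two sessions in random order with assessments before, during and after stimulation (section 3). The sample size rests on precedent (15-20 patients), with no calculation, so there is no planned error rate or power to reproduce.

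**Assumptions.** Two-sided 5%; sphericity; one pre-stimulation value with the same error variance as each post value; within-patient SD s. True means are (before, real, sham) = (0, g, g), with g in units of s, so there is no real-sham difference.

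**Overall F.** Degrees of freedom are 2 and 2 × 19 = 38. The squared deviations of (0, g, g) from their mean sum to (2/3)g², so the noncentrality is 20 × (2/3) × g²: 0, 0.83, 3.33, 7.50 and 13.33 at g = 0, 0.25, 0.5, 0.75 and 1.

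**Real versus before.** The paired difference has variance 2s². The test is a t with 19 df and noncentrality g√20/√2 = g√10: 0, 0.79, 1.58, 2.37 and 3.16.

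**Real versus sham.** The noncentrality is 0 for every g.

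The first two rows and the last follow from these formulas, and simulation agrees. The other two rows are simulated (60,000 trials).

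| What is taken as evidence of a tDCS effect | g = 0 | 0.25 | 0.5 | 0.75 | 1 |
|---|---|---|---|---|---|
| Overall F | 5% | 11% | 33% | 65% | 89% |
| Real versus before | 5% | 12% | 32% | 61% | 85% |
| Real differs from before, sham does not | 4% | 8% | 15% | 16% | 9% |
| Overall F, then real versus sham | 2.3% | 2.9% | 4.2% | 4.8% | 5.1% |
| Real minus sham alone | 5% | 5% | 5% | 5% | 5% |

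**If the two baselines are averaged.** With the same independent errors, the variance of real minus before falls from 2s² to 1.5s² and the noncentrality becomes g√(20/1.5). The real-versus-before rates at g = 0.25 to 1 rise to 14%, 41%, 74% and 93%. Sphericity then fails, so the overall-F row no longer applies exactly.

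**Power also depends on the unstated procedure.** Take a real-sham difference of 0.66 SD of the paired difference, which a direct paired test detects with 80% power at n = 20. Over shared gains of 0 to 1 SD, power is 76-80% for F followed by unadjusted pairs, 67-78% for Holm over three pairs, and about 63% for F plus Bonferroni.

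**The case against.** The strongest reply is that this is under-specification and not an invalid analysis. Random order, a sham procedure and patient blinding all point to real versus sham as the intended comparison, and an analyst who followed the F test with that contrast would be safe, at 2.3-5.1% in the table. That is correct. The point is only that no section commits to it.

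A second reply is that section 8.2 does not state its factors. A session-type by time ANOVA, with each post value set against its own session baseline, could also fit the wording, and its interaction term would not respond to a shared gain. This too is fair: the overall-F rates belong to the three-condition reading. On the other reading the time main effect still responds to a shared gain, and the deciding term is still not named.

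Third, the inflation is conditional. The documents give no size for a practice or placebo gain, and at zero gain the rate is 5%. So the table is a range and not a forecast. The handling of the baselines changes its figures but not their direction.

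Finally, naming the contrast would by itself cure the defect, and baseline adjustment brings in a carryover assumption. That is why the fix below pairs the adjustment with an unadjusted sensitivity analysis.

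**Conclusion.** The concern holds and should be fixed before results are seen. Section 8.2 names no deciding test, and two of the results it would naturally produce can be significant with no effect of tDCS beyond sham. Under the assumptions above, the false-positive rate of a tDCS claim is about 5% for real minus sham. For a shared gain of 0.25 to 1 within-patient SD it is 11% to 89% for the overall F and 12% to 85% for real versus before. There is no inflation if no gain is shared. The missing commitment does not depend on the size of that gain. The design and the planned data already support the right test.

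**What to change.** State in section 8.2 that the primary test is the within-patient real-minus-sham difference in the post-stimulation minimum detectable ankle angle, two-sided at 5%, reported with its 95% CI. Estimate it by a crossover analysis with a session term, adjusted for the difference between the two session baselines. Label the overall F and all comparisons with before as descriptive.

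Define one ankle value per patient and session, for example the mean of the dorsiflexion and plantar-flexion values, since the endpoint covers both. Say which foot is used, because section 6.2.1 leaves it open, and align the endpoint in section 2.2.

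The adjustment assumes that session-1 stimulation does not carry over into the session-2 baseline. Section 1.2 says "the effects of tDCS on sensation can last for several minutes", but section 3 gives no interval between sessions. State the assumption and report the estimate without baseline adjustment as a sensitivity analysis. With a correlation of 0.5 between the between-session pre and post differences, suppose 25% or 50% of the real effect remains in the session-2 baseline:
- If it is gone by the post value, the adjusted estimate is 6% or 13% too large and the unadjusted one is unbiased.
- If it also remains in the post value, the adjusted estimate is 6% or 12% too small and the unadjusted one 13% or 25% too small.

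With no true effect there is nothing to carry over, so the type I error is unchanged.

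The cost is wording and two error degrees of freedom (19 to 17), with no added patients, visits or measurements. Against 80% power unadjusted, simulated power with adjustment and a 10:10 order split is 77%, 81%, 88% and 96% at correlations of 0, 0.3, 0.5 and 0.7, so the loss is about 2-3 points if the baselines carry no information. A balanced 10:10 order list is optional.

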6.2. Outcome Assessments

6.2.1. Proprioception Measurement

Both minimum detectable change in joint position and position matching techniques will be used.

For minimum detectable change in joint position of the ankle, subject's foot will be placed on a foot pad with adjustable angle. The starting angle will be parallel to the floor. The angle will be changed by 2 degrees in each step and subject will be asked to report as soon as they feel a movement in their ankle with their eyes closed. Direction of movement will be at both dorsiflexion and plantar flexion.

For the matching position of the ankle, the footpad will be positioned in various angles ranging from 5 degree to 45 degree and will be asked to try to match the ankle on the other side with their eyes closed. The angle on the other foot will be measured and recorded. For the same-

side matching, subjects will be asked to remember than angle and try to reproduce it after the ankle is returned to the neutral position.

For measuring proprioception at the big toe, the experimenter will move the toe with steps of 2 degrees at a time and will ask subject to report any change as soon as felt with their eyes closed.

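### Section 8.2 analyses a two-session crossover without naming real versus sham as the contrast, the source of the before value, or a session term, and no balancing of order is stated

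*Combined protocol and SAP*

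**What the plan says.** Section 3 sets out a crossover: "Subjects will be asked to participate in 2 sessions". The order is random: "In one of the sessions, decided randomly, the sham stimulation will be applied and during the other session the real tDCS stimulation will be applied". No blocking or other balancing of order is stated. Measurements are repeated within each session: "Similar sets of assessments will be performed before, during and after application of real or sham stimulations". Each patient therefore has two pre-stimulation values.

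Section 8.2 is a single sentence: "A repeated measure ANOVA will be used to compare the outcome measures before the stimulation, after the real stimulation and after the Sham stimulation". Section 1.2 words the comparison the same way, "to compare in these subjects before the stimulation and after the real and sham stimulation". Neither place names a contrast between real and sham, a term for session 1 or 2, or which session's pre-stimulation value is used.

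Section 8.1 gives the size, "We plan to recruit 20 patients in this study", from precedent in the literature. It states no effect size, SD, alpha or power. The primary endpoint, the ankle detection angle, is measured by a fixed routine in Section 6.2.1: "The starting angle will be parallel to the floor. The angle will be changed by 2 degrees in each step".

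**The concern.** In a two-session crossover the question is whether the after-stimulation result differs between real and sham. A three-level ANOVA mixes that with a different question, whether *before* differs from *after*. A second visit can change results without any stimulation effect. This is plausible for the ankle test, which repeats the same start angle and step size. If the *before* level comes only from the first session, such a change separates it from both *after* levels, and the overall F test can be significant when stimulation does nothing.

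The same change also adds noise to real versus sham when no session term removes it, and an uneven split of orders displaces the estimate. Pooling the error over the three levels has a further weakness: it assumes equal variances and equal correlations, and the unstated choice of *before* value can break that assumption.

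**Working it through.** **Inputs from the documents:** 20 patients (8.1); two sessions in random order (3); pre-stimulation values in both sessions (3); levels before, after real and after sham (8.2). The documents give no power figure to reproduce.

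**Assumptions:** two-sided 5%; σ is the residual SD of one measurement once the patient's own level is removed; δ is session 2 minus session 1 in units of σ, taken as 0, 0.25 and 0.5; standardised paired effect dz = 0.66, which gives 80% power at n = 20 and equals 0.66 × √2 = 0.93σ. If σ were one 2-degree step, the non-zero shifts would be 0.5 and 1 degree. Order is taken as coin tosses unless a split is given.

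**1. Omnibus F with no treatment effect.** With *before* from session 1, the expected means are 0, δ/2 and δ/2, and their average is δ/3. The noncentrality is 20 × [(δ/3)² + 2(δ/6)²] = 20δ²/6, which is 0.21 at δ = 0.25 and 0.83 at δ = 0.5. Simulated rejection is 6.5% and 10.8%. At exactly 10:10 it is still 6.2% and 9.8%, so balance does not remove it. With *before* as the mean of both sessions, all three means are δ/2 and rejection stays at about 5%.

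**2. Pooled-error contrast with no shift.** The expected error mean square is the average variance minus the average covariance of the three levels.
- *Before* from session 1, within-session correlation 0.5 (assumed): over random orders *before* has average covariance 0.25 with each *after* level, so 1 − (0.25 + 0.25 + 0)/3 = 0.83.
- *Before* as the mean of both sessions, independent residuals: (0.5 + 1 + 1)/3 = 0.83.

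Real versus sham needs 1. The standard error is too small by √0.83 = 0.91, and simulated type I error is about 7% in both cases.

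**3. Real versus sham and the shift.** Write each paired difference as d = 0.93 + sδ + e, with s = +1 if real is in session 2 and −1 otherwise, and Var(e) = 2. The mean of s is (n1 − n2)/20. Over random orders this averages zero, so there is no average bias. At a realised 13:7 the estimate moves by 6/20 = 0.30 of the shift. Coin tosses give 13:7 or worse with probability 26%. Paired power at 13:7 is 72% or 85% at δ = 0.25, and 61% or 88% at δ = 0.5, depending on direction.

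Averaged over orders, the variance of d is multiplied by 1 + δ²/2, which is 1.03 and 1.13 at δ = 0.25 and 0.5. Paired type I error stays at 5.0%.

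**4. With a period term.** The variance factor is (1/n1 + 1/n2)/4 on 18 degrees of freedom, whatever the shift. Power is 79.7% at 10:10, 75.9% at 13:7, 72.5% at 14:6 and 77.5% averaged over coin tosses.

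| δ | Omnibus F rejects, no effect, *before* from session 1 | Power, paired | Power, pooled ANOVA contrast | Power, period term at 10:10 |
|---|---|---|---|---|
| 0 | 5.0% | 80.0% | 81.9% | 79.7% |
| 0.25 | 6.5% | 78.7% | 81.3% | 79.7% |
| 0.5 | 10.8% | 75.1% | 79.1% | 79.7% |

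The pooled column assumes independent residuals and *before* from session 1. Under those conditions its type I error is 5.0%, 5.2% and 5.6%.

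**The case against.** The shift is assumed. The documents give neither a shift nor an SD. Patients are tested before and during stimulation ahead of the first *after* value, so much of any practice effect may be spent by then. Nothing in the documents suggests a shift for the tuning fork or the walk. This stands, and it limits every size given here.

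The plan names an ANOVA, not a paired test. Against the pooled ANOVA contrast the proposed model is about 2 points worse with no shift, 1.6 worse at 0.25 SD and 0.6 better at 0.5 SD. This also stands. The 4.6-point gain at 0.5 SD (79.7% against 75.1%) is over the paired test only. The pooled contrast's advantage needs independent residuals and a single-session *before* value, and the plan assures neither.

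Section 8.2 is silent rather than exclusive. Change from each session's own pre-stimulation value would cancel an additive shift. That reading is possible but not stated, and it has a price: the variance becomes 4(1 − ρ) instead of 2, which is double at ρ = 0 (about 51% power) and equal only at ρ = 0.5 (about 80%). Likewise, random order need not mean coin tosses, and the 26% depends on that assumption.

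A reader might infer that omitting the period term biases real versus sham, or is the main source of false positives. The documents do not support either. Random order makes the average bias zero, and the omnibus problem comes from the unnamed contrast and the unstated *before* value.

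**Conclusion.** The point holds as a specification gap of modest size. Its main part is that Section 8.2 neither names real versus sham as the effect nor says which *before* value enters. Depending on that unstated choice, either the omnibus test can reject without a treatment effect (about 6.5% and 11% at assumed shifts of 0.25 and 0.5 residual SD), or the pooled contrast runs at about 7% type I error with no shift at all.

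The missing session term and the unstated balancing are the lesser part. Averaged over coin-toss orders they cost 1.3 points of paired power at 0.25 SD (80.0 − 78.7) and 4.9 at 0.5 SD (80.0 − 75.1). On the pooled contrast the loss is 0.6 and 2.8 points. All of this rests on the assumed shift, dz = 0.66 and a two-sided 5% level. Carry-over is a separate question that this check does not touch.

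**What to change.** In Section 8.2, write: *The treatment effect for each endpoint is real versus sham, estimated from the after-stimulation values in a model with patient, treatment and period (session 1 or 2). Before-versus-after comparisons are reported separately and are not read as the treatment effect.* Each session's own pre-stimulation value may be added as a covariate. It costs one degree of freedom and helps only if it correlates with the after value.

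In Section 3, write: *Session order is allocated from a concealed computer-generated list of permuted blocks (two of 4 and two of 6 in random order, total 20), aiming for 10 patients per order.*

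Adopt the two together. The term alone under coin-toss order averages 77.5% power, below the 78.7% of the unadjusted paired contrast at a 0.25 SD shift. Balance alone leaves the shift in the error: paired power at 10:10 without the term is 76.2% at 0.5 SD.

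The cost is one list and a rewritten model sentence, with no extra patients. With no shift, the power cost is about 0.3 points against the paired contrast (80.0% to 79.7%), or about 2 points against the pooled contrast (81.9% to 79.7%) if residuals are independent. If two patients in one order drop out (10:8), the term costs 0.8 points (75.2% to 74.3%, from unrounded values). The change does not address carry-over.
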